4.1 Clinical Efficacy

The assessment of Clinical Efficacy is the Primary Objective of Phase 2 and the Secondary Objective of Phase 1 of the study and will be performed by RECIST 1.1 and irRECIST.

4.1.1 Endpoints & Assessment Methods

Clinical Efficacy is determined by measuring the Progression-free Survival (PFS), Overall Response Rate (ORR), and Overall Survival (OS). Every attempt should be made to use whichever imaging technique(s) and test(s) are used initially for repeat evaluations throughout the study, whereby the last tumor assessment will be at least 4 weeks from the prior assessment.

4.1.1.1 Progression-free Survival Rate

The proportion of subjects who survive and do not progress - Progression Free Survival (PFS) rate- within the first 6 months of treatment based on RECIST v1.1 evaluated for the per-protocol analysis population constitutes the primary endpoint in Phase 2 of the study. PFS rate at 6 months will be based on disease assessments at the scheduled visit at the start of Cycle 7.

4.1.1.2 Progression-free Survival Time

Progression-free survival time will be defined as the number of days from the date of first dose to the date of earliest disease progression based on RECIST v1.1 and irRECIST, or to the date of death, if disease progression does not occur.

CONFIDENTIAL

4.1.1.3 Overall Response Rate

Overall Response Rate is defined as the percentage of subjects meeting criteria of CR or PR over a period of at least 4 weeks.

4.1.1.4 Overall Disease Control Rate

Disease Control is defined as SD, PR or CR over a period of at least 4 weeks.

4.1.1.5 Overall Survival Time

Overall survival (OS) time will be measured for each subject with time origin at the date of study Day 1 until recorded date of death or last follow-up. Subjects lost to follow-up will be censored on the date when they were last known to be alive. Every effort will be made to follow subjects for overall survival after they complete or discontinue the study.

4.1.2 Subject Evaluation & Statistics

The Per-Protocol (PP) Population for clinical efficacy is defined as all subjects who received at least 75% of the scheduled doses of MEDI4736, motolimod (pre Amendment 2), and PLD over the first 2 cycles, as well as respective disease assessments, without major protocol violations. The Intent-To-Treat (ITT) Population for clinical efficacy is defined as all subjects who receive at least one dose of PLD, motolimod (pre Amendment 2) or MEDI4736.

The analysis of clinical efficacy will be based on both the intent-to-treat (ITT) and the per-protocol (PP) populations.

The PFS Rate at 6 months based on RECIST v1.1 evaluated for the per-protocol analysis population constitutes the primary endpoint in Phase 2 of the study. This PFS rate along with its one sided 95% Confidence Interval (CI) based on binomial distribution will be estimated and reported. The one-sided null hypothesis of 6-month PFS ≤ 0.25 will be rejected at 0.05 level of significance if the 95% one-sided CI does not contain 0.25. The 12-months PFS rate along with its 95% one-sided CI will be calculated and reported as a secondary endpoint.

Tumor Response will be summarized and analyzed descriptively for each cohort and analysis population. A 95% Confidence Interval based on binomial distribution will be constructed for the estimated ORR.

Median OS will be calculated using the Kaplan-Meier method. The analysis of PFS and OS will be updated based on data collected during the Post Study Follow-up (see Section 3.1.16).

4.2 Safety and Tolerability

The assessment of safety and tolerability is the Primary Objective of Phase 1 and Secondary Objective of Phase 2 of the study. It will be performed by the internal data safety monitoring panel on an ongoing basis, based on data review and regular conference calls with the investigators. In Phase 1, formal safety reviews will be performed and documented for the purpose of dose escalation / de-escalation in the context of the 3+3 study design.

4.2.1 Endpoints & Assessment Methods

Laboratory tests, vital sign measurements, physical exams and subject interviews will be performed to detect new abnormalities and deteriorations of any pre-existing conditions. The investigator will evaluate any laboratory abnormalities for clinical significance, and clinically significant abnormalities will be recorded as adverse events. All clinically significant abnormalities and deteriorations from time of signing of informed consent to the end of study visit should be recorded in the Case Report Forms as adverse events and graded according to the National Cancer Institute Common Terminology Criteria for Adverse Events (CTCAE), version 4.03.

4.2.2 Subject Evaluation & Statistics

The Per-Protocol (PP) Population for DLT Assessment includes:

- All subjects who experience a DLT at any time during the DLT Evaluation Period (as defined in Section 3.1.9)
- All subjects with no DLT who receive at least 75% of the scheduled doses of MEDI4736, motolimod (pre Amendment 2), and PLD as well as respective safety assessments, without major protocol violations, over the entire DLT Evaluation Period (as defined in Section 3.1.9).

Refer to Section 3.1.11 for subject replacements.

The Intent-To-Treat (ITT) Population for safety and tolerability is defined as all subjects who receive at least one dose of PLD, motolimod (pre Amendment 2) or MEDI4736.

In Phase 1, for the primary endpoint of determining DLTs and the MTD, the analysis of safety and tolerability will be based on the PP Population for DLT Assessment.

In both Phases 1 and 2, the overall analysis of safety and tolerability will be based on the ITT Population for safety and tolerability.

Appropriate summaries of AEs, laboratory data and vital sign data will be presented. Adverse events will be coded using the MedDRA dictionary. Incidences of treatment-emergent adverse events (TEAE, those events that started after dosing or worsened in severity after dosing) will be presented overall and by maximum severity (according to CTCAE version 4.03) and relationship to study medication.

For each continuous laboratory parameter, results will be categorized as low, normal, or high based on the laboratory normal ranges. Frequencies and percentages will be presented by treatment arm for the shifts in these categories (i.e., low to normal, low to high, high to low, etc.) from baseline to each post-treatment assessment time point. Additionally, for each continuous hematology and chemistry parameter, descriptive statistics will be presented by treatment arm for the changes from baseline to each post-treatment assessment time point. Descriptive statistics will be presented by cohort for the changes in vital signs from baseline to each post-treatment assessment time point.

4.3 Biological Activity

Samples for exploratory assessment of correlative immunologic research will be collected according to the Study Flowchart in Section 3.2. Assessments include, but are not limited to: Phenotypic analysis of PBMCs, Characterization of MDSCs, Quantification of tumor-specific T-cell responses, Immune Landscape: Tumor Infiltrating Lymphocytes and Tumor Microenvironment, TCR sequencing, Immune Biomarkers, Pharmacogenomics, and BRCA status of tumors.

A comprehensive list of variables to be analyzed for the exploratory assessment of correlative immunologic research is located in Section 8.7.

4.3.1 Endpoints & Assessment Methods

Subjects who received at least one dose of PLD, motolimod (pre Amendment 2) or MEDI4736, and provide baseline and at least one post-treatment sample, will be evaluated. The assessment methods are described in the respective appendices for each assay.

4.3.2 Subject Evaluation & Statistics

The association of clinical activity with tumor markers will be assessed based on PD-L1 expression level and changes in tumor-infiltrating lymphocytes (TIL) from mandatory pre- and post-treatment biopsies in the Phase 2 cohort. Subjects will be classified as responders or non-responders based on RECIST v1.1 and irRECIST criteria. Within each response group, subject tumors will be assessed as positive or negative for PD-L1 expression. Fisher's Exact test will be used to test whether there is a significant association between responder-status and PD-L1 expression. Assuming evaluable tumor biopsies are available for at least 36 subjects and approximately equal numbers of responders and non-responders, if there are 80% and 30% of subjects with positive PD-L1 expression in the two groups, respectively, there will be at least 80% power to detect a significant difference. A 95% confidence interval for the odds ratio for positive PD-L1 expression will be presented. The association between response and TIL changes (increase, decrease, or no change) will be evaluated similarly.

Results from the remaining correlative studies will be summarized descriptively and evaluated in relation to outcome. All data will be provided in subject data listings.

5 Subject Eligibility

Note: Standard of Care procedures may be used for eligibility assessments provided they meet the criteria specified in either the inclusion criteria or flowchart.

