5.1 Inclusion Criteria

Eligible subjects ***must fulfill*** all of the following criteria:

1.	
Subjects must have recurrent or persistent platinum-resistant epithelial ovarian, fallopian tube, or primary peritoneal carcinoma with measurable disease (as defined by RECIST 1.1.) after first or second line platinum-based chemotherapy, for which treatment with PLD is indicated.
 
Platinum-based therapy is defined as treatment with carboplatin, cisplatin or another organoplatinum compound.
 
Platinum-resistant is defined as having a platinum-free interval (PFI) of < 12 months after first- or second-line platinum-based chemotherapy, or having disease progression while receiving second-line platinum-based chemotherapy.
 
Subjects are allowed to have received, but are not required to have received:
 
 • one additional cytotoxic regimen and/or PARP inhibitor for management of recurrent or persistent disease. • biologic therapy (e.g., bevacizumab) as part of their primary treatment regimen or as part of their treatment for management of recurrent or persistent disease. 														
2.	Histologic documentation of the original primary tumor .														
3.	Documented radiographic disease progression < 12 months after the last dose of first- or second-line platinum-based chemotherapy.														
4.	
Subjects in Phase 2 must have disease amenable to biopsy and must be willing to undergo pre- and post-treatment tumor biopsies (see Section 3.2 for biopsy time points). Optional for Phase 1.
 
NOTE: Archival tissue will be requested for all subjects, preferably from primary tumor site prior to cancer treatment; however, archival tissue is not a requirement for study entry.
														
5.	ECOG performance status of 0 or 1.														

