8.7.5 Immune Landscape: TILs and Tumor Microenvironment

Immunohistochemistry (IHC): Unstained sections of tumor will be analyzed by The Center of Experimental Therapeutics in Lausanne, Switzerland, where an immune signature will be assessed using a multiplexed immunohistochemical approach followed by multispectral imaging and unmixing. Multispectral imaging and linear unmixing offers the ability to analyze in a comprehensive, spatially oriented and quantitative fashion tumor slides, each stained with multiple antibodies, in either a brightfield (up to 3-4 antibodies + counterstain) or fluorescence (up to 6-8 antibodies + counterstain + autofluorescence removal) mode. More specifically, lineage specific markers i.e. CD3, CD4, CD8 for T lymphocytes (and FoxP3 for Tregs), combined with markers of activation, or functional exhaustion, for example CD45RO, CD38, HLA-DR, TIA-1, granzyme-B, Ki67, PD-1, ICOS, LAG-3, Tim-3 and/or CTLA-4 will be used. Furthermore, the spatial distribution of immune cell subsets with the level of expression on tumor cells of major components of the antigen presenting machinery i.e. HLA class I and II molecules, β 2 microglobulin, tapasin, and TAP1 and 2 will be evaluated. Tumor cells and the whole microenvironment can also be interrogated for immunosuppressive factors such expression of PD-L1 and PD-L2, TGF-b, IL-10, COX1 and 2, IDO-1 etc. Tumor cells can be interrogated for proliferation (Ki67), apoptosis (cleaved caspase-3), necrosis (HMGB1) or autophagy (beclin, LC3). Finally, innate cells can be characterized, for example by CD68 and CD163 for M1 and M2

CONFIDENTIAL

macrophages, CD33 for MDSCs and NKp46 for NK cells. Finally, the vasculature will be interrogated using several markers of activated and tumor endothelium and pericytes.

As a complementary approach to the IHC, Nanostring platform will be used to assess the mRNA expression level of genes reflecting tumor microenvironment signatures, including genes of innate and adaptive immunity, inflammation, wound healing and angiogenesis.

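### Protocol 4.3.2 sorts a quantitative TIL change into three classes with no stated no-change band; a rank test on the measured change would use the paired biopsies better

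*Protocol*

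**What the plan says.** Protocol 4.3.2 sets out two biomarker associations with response that are to be tested. The first is PD-L1 status: "Fisher's Exact test will be used to test whether there is a significant association between responder-status and PD-L1 expression". Its power statement assumes "Assuming evaluable tumor biopsies are available for at least 36 subjects and approximately equal numbers of responders and non-responders", positivity of 80% and 30% in the two groups, and concludes that "there will be at least 80% power to detect a significant difference". The second is TIL change, covered in one sentence: "The association between response and TIL changes (increase, decrease, or no change) will be evaluated similarly". No test is named for TIL, no power is given, and no rule separates no change from an increase or a decrease. The remaining correlative results are to be summarised descriptively and related to outcome.

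Protocol 8.7.5 says the imaging method can "analyze in a comprehensive, spatially oriented and quantitative fashion tumor slides" and lists many markers, including CD3, CD4, CD8 and FoxP3. It does not say which cell population or tissue compartment is the TIL measure. Under Protocol 5.1, Phase 2 subjects "must be willing to undergo pre- and post-treatment tumor biopsies". The flowcharts in Protocol 3.2 place these at screening and Cycle 2 Day 1.

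SAP 2.2.5 and 3.3.3 state that the immunological data are analysed by another entity, outside the SAP's analysis sections. Part of that text is redacted.

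**The concern.** A quantitative change is reduced to three classes and then, on the natural reading, compared with a test that ignores their order. Each step costs power. Forming classes discards the size of the change. An unordered test treats decrease, no change and increase as labels, although the question is directional.

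The width of the no-change class is also open. On a quantitative scale almost no pair of biopsies is exactly equal, so the class needs a tolerance band. If the band is not fixed before response data are linked, an analyst could try several and keep the one with the smallest p-value.

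At stake is one of only two tested biomarker associations, on tissue that Phase 2 subjects give through required invasive sampling. A real association could be missed, or a chance one reported.

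**Working it through.** **Inputs from the documents**
- 36 evaluable subjects in about equal groups; PD-L1 positivity 80% and 30% (Protocol 4.3.2).
- 41 Phase 2 subjects, 6 of them from Phase 1 (Protocol 3.1.5), where biopsy was optional. This leaves 41 − 6 = 35 with required biopsies.
- Second-line response in platinum-resistant disease of 15-20% (Protocol 1.1). With 20%, 35 × 0.20 = 7 responders, a 7:28 split.

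**Assumptions, because the documents are silent**
- Two-sided alpha of 0.05, in line with the planned 95% interval for the odds ratio.
- Log change normal with SD 1 in both groups; non-responders centred at 0, responders at d.
- Fisher's test in its three-class (Freeman-Halton) form.
- Change is called when it exceeds ±w, with w = 0, 0.25, 0.5, 0.75 or 1.0 SD.

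**Step 1: the plan's own figure.** Power = Σₐ Σ_b Bin(a; 18, 0.80) · Bin(b; 18, 0.30) · 1[Fisher p(a, b) ≤ 0.05] = 0.835. The stated figure of at least 80% is reproduced. It concerns PD-L1 only.

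**Step 2: an effect on the same scale.** On a normal scale, 80% against 30% corresponds to d = Φ⁻¹(0.80) − Φ⁻¹(0.30) = 0.842 + 0.524 = 1.37 SD. A shift of 1 SD is the other main case, since the Wilcoxon test then has close to 80% power with equal groups.

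**Step 3: simulated power at d = 1 SD, over the five bands**

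| Split | Three-class Fisher | Wilcoxon | Difference (points) |
|---|---|---|---|
| 18:18 | 48-59% | 81% | 81 − 59 = 22 to 81 − 48 = 33 |
| 17:18 | 50-59% | 79% | 20 to 29 |
| 9:26 | 37-42% | 67% | 25 to 30 |
| 7:28 | 28-33% | 60% | 27 to 32 |

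**Step 4: sensitivity**
- d = 1.37, 18:18: Wilcoxon 97%, loss about 12 to 25 points, so the three-class test keeps about 72-85%. The top of the loss range is the zero-width band; with bands of 0.25 SD or wider the loss is 12 to 17.
- d = 1.37, unequal groups: loss 25 to 29 points at 9:27 (bands 0.25 to 1.0) and 84.8 − 58.9 = 26 to 84.8 − 47.1 = 38 at 7:29.
- Where zero lies matters. If responders rise and non-responders fall by equal amounts (bands 0.25 to 1.0), the loss is 18 to 25 points at 18:18 and 15 to 22 at 9:27 for d = 1. It is 8 to 12 at 18:18 for d = 1.37.
- Keeping the classes but using an ordered rank test recovers part of the loss. At 18:18 and d = 1 (bands 0.25 to 1.0) the loss falls from 21-25 to 9-13 points with the normal-approximation test. An exact ordered test recovers about 7 to 10 points.

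**Step 5: choosing the band afterwards.** With d = 0, taking the smallest p-value over the five bands rejects in about 12-16% of trials, against a nominal 5%. With four bands (0.25 to 1.0) at 18:18 the figure is 11.4%.

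**The case against.** Several points on the other side stand. The documents give no SD, effect size or band for TIL change, so no single power loss can be attributed to the plan. At the only effect size that 4.3.2 offers, borrowed from PD-L1, the three-class test remains adequately powered with equal groups and any reasonable band. A reader might infer that most of the information in the biopsies is thrown away. That is not shown: part of the loss comes from ignoring order, not from forming classes, and Protocol 4.3.2 promises subject listings of all data.

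Fisher's test for TIL is an inference from the reference back to PD-L1, though the natural one. Naming a no-change class implies some tolerance, so a reader who takes the class to be literally empty goes too far. A band may also be set in redacted text or in the other entity's plan. A reader might further infer that the band will be chosen after the fact. The documents show no such intention; they only do not, in readable form, rule it out.

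Finally, Protocol 4.3 describes this work as exploratory. That limits the weight of the point but does not answer it, because a better analysis of the same samples is available at almost no cost.

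**Conclusion.** The concern holds as a minor, exploratory item. The protocol states a three-class comparison of a quantitative change, with the classes undefined in the readable text and a test that most naturally ignores their order. Under the stated assumptions the cost is about 20 to 33 points of power at a 1 SD shift. At 1.37 SD with equal groups it is about 12 to 25 points, and larger with unequal groups. It is smaller if the two groups move in opposite directions from zero. A fixed loss of 20 to 30 points should not be quoted without these conditions.

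The 12-16% false-positive rate describes what would happen if the best of five bands were selected after seeing the data. It is a risk that prior specification removes, not a forecast. The primary endpoint, the 41-subject sample size, the MTD and the safety analyses are untouched.

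**What to change.** In Protocol 4.3.2, or in the correlative analysis plan with a reference from 4.3.2:
- Name one TIL measure in advance: the cell population and the tissue compartment. Without this, a change of test leaves the larger analyst choice open.
- Define change as the log ratio of the Cycle 2 Day 1 value to baseline, with a pre-stated offset for zeros.
- Test its association with response by an exact Wilcoxon rank-sum test, two-sided at 0.05, and report the Hodges-Lehmann shift with a 95% confidence interval.
- Keep increase, decrease and no change as a descriptive table only, with the band set from assay repeatability before response data are linked.

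If the other entity's plan already does this, a citation to it is enough. The cost is a few sentences, plus agreement on the measure, the offset and the band. No new samples or tissue assays are needed if repeatability data exist.

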5.1 Inclusion Criteria

Eligible subjects ***must fulfill*** all of the following criteria:

1.	
Subjects must have recurrent or persistent platinum-resistant epithelial ovarian, fallopian tube, or primary peritoneal carcinoma with measurable disease (as defined by RECIST 1.1.) after first or second line platinum-based chemotherapy, for which treatment with PLD is indicated.
 
Platinum-based therapy is defined as treatment with carboplatin, cisplatin or another organoplatinum compound.
 
Platinum-resistant is defined as having a platinum-free interval (PFI) of < 12 months after first- or second-line platinum-based chemotherapy, or having disease progression while receiving second-line platinum-based chemotherapy.
 
Subjects are allowed to have received, but are not required to have received:
 
 • one additional cytotoxic regimen and/or PARP inhibitor for management of recurrent or persistent disease. • biologic therapy (e.g., bevacizumab) as part of their primary treatment regimen or as part of their treatment for management of recurrent or persistent disease. 														
2.	Histologic documentation of the original primary tumor .														
3.	Documented radiographic disease progression < 12 months after the last dose of first- or second-line platinum-based chemotherapy.														
4.	
Subjects in Phase 2 must have disease amenable to biopsy and must be willing to undergo pre- and post-treatment tumor biopsies (see Section 3.2 for biopsy time points). Optional for Phase 1.
 
NOTE: Archival tissue will be requested for all subjects, preferably from primary tumor site prior to cancer treatment; however, archival tissue is not a requirement for study entry.
														
5.	ECOG performance status of 0 or 1.														
6.	
Laboratory parameters for vital functions should be in the normal range. Laboratory abnormalities that are not clinically significant are generally permitted, except for the following laboratory parameters, which must be within the ranges specified, regardless of clinical significance:
 
 
 Hemoglobin	≥ 9 g/dL	
 
 Neutrophil count	≥ 1.5 x 10⁹/L	
 
 Platelet count	≥ 100,000/mm³	
 
 Serum creatinine, or Creatinine Clearance	≤ 1.5x Institutional Upper Limit of Normal (ULN), or ≥ 50 mL/min (by Cockcroft-Gault formula)	
 
 Serum bilirubin	≤ 1.2 mg/dL	
 
 AST/ALT	≤ 2.5 x ULN	
 
 Alkaline phosphatase	≤ 2.5 x ULN	
 
	Hemoglobin	≥ 9 g/dL	Neutrophil count	≥ 1.5 x 10 ⁹ /L	Platelet count	≥ 100,000/mm ³	Serum creatinine, or Creatinine Clearance	≤ 1.5x Institutional Upper Limit of Normal (ULN), or ≥ 50 mL/min (by Cockcroft-Gault formula)	Serum bilirubin	≤ 1.2 mg/dL	AST/ALT	≤ 2.5 x ULN	Alkaline phosphatase	≤ 2.5 x ULN
Hemoglobin	≥ 9 g/dL														
Neutrophil count	≥ 1.5 x 10 ⁹ /L														
Platelet count	≥ 100,000/mm ³														
Serum creatinine, or Creatinine Clearance	≤ 1.5x Institutional Upper Limit of Normal (ULN), or ≥ 50 mL/min (by Cockcroft-Gault formula)														
Serum bilirubin	≤ 1.2 mg/dL														
AST/ALT	≤ 2.5 x ULN														
Alkaline phosphatase	≤ 2.5 x ULN														
7.	Age ≥18 years.														

CONFIDENTIAL

8.	Able and willing to give valid written informed consent.
9.	Body weight > 30 kg

